6.3.3. Part 2 (Weeks 1-24)

All study visits are to be scheduled relative to the Part 2 Day 1 visit date. Visit windows are ± 4 days of the protocol-specified date through Week 24

The following will be performed at the Part 2 visits from Part 2 Week 1 up to Week 24:

- Review concomitant medications
- Record any SAEs and all AEs related to protocol mandated procedures occurring after signing of the consent form.
- Complete physical examination (urogenital/anorectal exams will be performed at the discretion of the Investigator) (**Day 1, Weeks 12 and 24**)
- Symptom-directed physical examination (**Weeks 1, 2, 4, 8, and 18**)

6.4. Post-Treatment Assessments

6.4.1. Early Study Drug Discontinuation Visit for Premature Discontinuation from Study

Subjects who discontinue study drug before Week 24 will be required to complete an ESDD visit within 72 hours of stopping study drug. Prior to Week 24, if a subject discontinues study dosing (for example, as a result of an AE), every attempt should be made to keep the subject in the study and continue to perform the required study-related follow-up and procedures (see Section 6.5, Criteria for Discontinuation of Study Treatment). If this is not possible or acceptable to the subject or investigator, the subject may be withdrawn from the study.

CCI

At the ESDD Visit, any evaluations showing abnormal results indicating that there is a possible or probable causal relationship with the study drug will be repeated weekly (or as often as deemed prudent by the Investigator) until the abnormality is resolved, returns to baseline (Day 1) value, or is otherwise explained.

The following evaluations are to be completed at the ESDD Visit:

- Review concomitant medications
- Record any SAEs and all AEs related to protocol mandated procedures occurring after signing of the consent form.
- Complete physical examination (urogenital/anorectal exams will be performed at the discretion of the Investigator)
- Vital signs measurement (blood pressure, pulse, respiration rate, and temperature), including weight
- Obtain blood and urine samples as described in Sections 6.8.1, 6.8.2, Appendix 2, and Appendix 3
- Collect subject dosing diary from all subjects
- Document study drug accountability for all study drug dispensed
- Document reason for discontinuation

6.4.2. 30 Day Follow-Up Visit

Subjects meeting criteria for sub-optimal virologic response in Part 1, defined as a reduction in plasma HIV RNA $\leq 0.5 \log_{10}$ from pre-GS-9131 baseline after 10 days for Sentinel Cohort 1 and after 14 days for Sentinel Cohort 2 of GS-9131 functional monotherapy, will be required to return to the clinic 30 days after the last dose of study drug for the 30-Day Follow-Up Visit.

Subjects who complete the study drug through Week 24 **CCI** [REDACTED] will be required to return to the clinic 30 days after the last dose of study drug for the 30-Day Follow-Up Visit.

Subjects who prematurely discontinue study drug prior to Week 24 visit of the Part 2 phase and refuse to continue in the study will be asked to return to the clinic 30 days after the completion of the ESDD Visit for the 30-Day Follow-Up Visit.

Those subjects who prematurely discontinue study drug prior to the Week 24 visit of the Part 2 phase and continue in the study through at least one subsequent visit after the ESDD Visit will not be required to complete the 30-Day Follow-Up Visit.

CCI [REDACTED]

CCI [REDACTED]

For the purpose of scheduling a 30-Day Follow-Up Visit, a ± 6 days window may be used. The following evaluations are to be completed at the 30-Day Follow-Up Visit:

- Review concomitant medications
- Record any SAEs and all AEs related to protocol mandated procedures occurring after signing of the consent form.
- Symptom-directed physical examination
- Vital signs measurement (blood pressure, pulse, respiration rate, and temperature), including weight
- Obtain blood and urine samples as described in Sections 6.8.1, 6.8.2, Appendix 2, and Appendix 3

At the 30-Day Follow-Up Visit, any evaluations showing abnormal results believed to be a reasonable possibility of a causal relationship with the study drugs will be repeated weekly (or as often as deemed prudent by the Investigator) until the abnormality is resolved, returns to baseline (Day 1) value, or is otherwise explained.

6.5. Criteria for Discontinuation of Study Treatment

Study medication will be discontinued in the following instances:

- Unacceptable toxicity, as defined by the toxicity management section of the protocol, or toxicity that, in the judgment of the investigator, compromises the ability to continue study-specific procedures or is considered to not be in the subject's best interest
- Subject request to discontinue for any reason
- Pregnancy during the study; refer to [Appendix 7](#)
- Development of active tuberculosis infection
- Discontinuation of the study at the request of Gilead, a regulatory agency or an institutional review board or independent ethics committee (IRB/IEC)

Study medication may be discontinued in the following instances:

- Intercurrent illness that would, in the judgment of the investigator, affect assessments of clinical status to a significant degree. Following resolution of intercurrent illness, the subject may resume study dosing at the discretion of the investigator.
- Lack of efficacy
- Subject noncompliance

6.5.1. Study Stopping Criteria

By Subject: Study drug dosing for a subject will be discontinued if that subject experiences a Grade 3 or Grade 4 treatment-emergent adverse event (AE) or confirmed laboratory abnormality judged by the study investigator to be possibly related to study drug, or any serious adverse event (SAE) considered to be possibly related to study drug.

By Sentinel Cohort: Study drug dosing during Part 1 for the Sentinel Cohorts will be discontinued if any of the following criteria is met:

- 2 or more subjects experiencing Grade 3 or Grade 4 treatment-emergent AEs judged by the study investigator to be possibly related to study drug, or
- 2 or more subjects experiencing confirmed Grade 3 or Grade 4 laboratory abnormalities, or
- 2 or more subjects experiencing any SAE that is considered to be possibly related to study drug.

For the Randomized Cohort and Part 2: If 2 or more subjects in Part 1 of the Randomized Cohort who are subsequently assigned to treatment cohorts in Part 2 experience a Grade 3 or 4 treatment emergent AE leading to study drug discontinuation or an SAE judged by the study investigator to be possibly related to study drug, the IDMC will be convened to review all preliminary safety data generated in subjects dosed to date.

Subjects will be followed as clinically indicated until the treatment-emergent AE or laboratory abnormality returns to baseline or is otherwise explained, whichever occurs first. Grade 3 and 4 laboratory abnormalities that are not confirmed by repeat testing will be managed according to the clinic's practice; a decision to reinitiate dosing may be made by Gilead in consultation with the investigator and after a safety review.

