Part 2:

GS-9131 + BIC + DRV + RTV Regimen (Sentinel Cohort 1)

Subjects in the Sentinel Cohort 1 who had a $> 0.5 \log_{10}$ decline in HIV-1 RNA in Part 1 will discontinue their current failing regimen and begin treatment with GS-9131 + BIC + DRV + RTV once daily for 24 weeks. Subjects who had a $\leq 0.5 \log_{10}$ decline in HIV-1 RNA are not eligible to continue onto Part 2 and will be discontinued from the study.

At their Day 1 visit for Part 2, AEs, concomitant medications, drug accountability, vital signs, physical examinations, HIV-1 RNA, estimated GFR, hematology, chemistry, CD4 cell count, and urinalysis will be performed.

All subjects will be required to visit the clinic on Day 1, and Weeks 1, 2, 4, 8, 12, 18, and 24. At each visit, AEs, concomitant medications, drug accountability, hematology, chemistry, HIV-1 RNA, CD4 cell count, vital signs, and estimated GFR will be evaluated. A fasting metabolic profile will be performed on Day 1, Week 12 and 24 visits. A complete physical examination will be done at Day 1, Week 12 and 24 visits. A symptom directed physical examination will be done at all other visits. Urinalysis will be performed at Day 1, and Week 4, 12, and 24 visits. Urine pregnancy test (females of childbearing potential only) will be done on Day 1, and Weeks 4, 8, 12, 18, and 24; positive urine pregnancy test will be confirmed with a serum pregnancy test.

CCI [REDACTED]

CCI [REDACTED]

GS-9131 + BIC + TAF (Sentinel Cohort 2 and Randomized Cohort)

Subjects in the Sentinel Cohort 2 or Randomized Cohort (A-C) who had a $> 0.5 \log_{10}$ decline in HIV-1 RNA in Part 1 will discontinue their current failing regimen and begin treatment with GS-9131 + BIC + TAF once daily for 24 weeks. Subjects who had a $\leq 0.5 \log_{10}$ decline in HIV-1 RNA are not eligible to continue onto Part 2 and will be discontinued from the study. Subjects in Randomized Cohort D will begin treatment with GS-9131(180 mg) + BIC (75 mg) + TAF (25 mg) once daily for 24 weeks after successful completion of Part 1.

At their Day 1 visit for Part 2, AEs, concomitant medications, drug accountability, vital signs, physical examinations, HIV-1 RNA, estimated GFR, hematology, chemistry, CD4 cell count, and urinalysis will be performed.

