All subjects will be required to visit the clinic on Day 1, and Weeks 1, 2, 4, 8, 12, 18, and 24. At each visit, AEs, concomitant medications, drug accountability, hematology, chemistry, HIV-1 RNA, CD4 cell count, vital signs, and estimated GFR will be evaluated. A fasting metabolic profile will be performed on Day 1, Week 12 and 24 visits. A complete physical examination will be done at Day 1, Week 12 and 24 visits. A symptom directed physical examination will be done at all other visits. Urinalysis will be performed at Day 1, and Week 4, 12, and 24 visits. Urine pregnancy test (females of childbearing potential only) will be done on Day 1, and Weeks 4, 8, 12, 18, and 24; positive urine pregnancy test will be confirmed with a serum pregnancy test.

CCI [REDACTED]

CCI [REDACTED]

CCI [REDACTED]

Protocol-Specific Stopping Rules

By Subject: Study drug dosing for a subject will be discontinued if that subject experiences a Grade 3 or Grade 4 treatment-emergent adverse event (AE) or confirmed laboratory abnormality judged by the study investigator to be possibly related to study drug, or any serious adverse event (SAE) considered to be possibly related to study drug.

By Sentinel Cohort: Study drug dosing for the Sentinel Cohorts will be discontinued if any of the following criteria is met:

- 2 or more subjects experiencing Grade 3 or Grade 4 treatment-emergent AEs judged by the study investigator to be possibly related to study drug, or
- 2 or more subjects experiencing confirmed Grade 3 or Grade 4 laboratory abnormalities, or
- 2 or more subjects experiencing any SAE that is considered to be possibly related to study drug.

For the Randomized Cohort and Part 2: If 2 or more subjects in the Randomized Cohort who are subsequently assigned to treatment cohorts in Part 2 experience a Grade 3 or 4 treatment-emergent AE leading to study drug discontinuation or an SAE judged by the study investigator to be possibly related to study drug, the IDMC will be convened to review all preliminary safety data generated in subjects dosed to date.

Subjects will be followed as clinically indicated until the treatment-emergent AE or laboratory abnormality returns to baseline or is otherwise explained, whichever occurs first. Grade 3 and 4 laboratory abnormalities that are not confirmed by repeat testing will be managed according to the clinic's practice; a decision to reinitiate dosing may be made by Gilead in consultation with the investigator and after a safety review.

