3.3. Study Treatments

Subjects who provide written consent and meet all eligibility criteria will be allocated to one of the following treatment groups as follows:

Part 1: GS-9131 Functional Monotherapy

Part 1 consists of 3 cohorts:

Sentinel Cohort 1:

Approximately 10 TE viremic HIV-1 subjects will be enrolled to receive open-label GS-9131 60 mg in addition to their current failing ARV regimen.

Sentinel Cohort 2:

Up to 10 TE viremic HIV-1 subjects will be enrolled to receive open-label GS-9131 180 mg in addition to their current failing ARV regimen.

Randomized Cohort:

Up to 48 subjects failing their current ARV regimen will be randomized to GS-9131 (up to 180 mg) or PTM. These drugs will be added to their failing regimen for 14 days described below. Doses and number of cohorts will be determined by data from Sentinel Cohort 2:

- Treatment Arms A-C: GS-9131 up to 180 mg once daily + current failing ART regimen (n=12 per cohort)
- Treatment Arm D: PTM GS-9131 + current failing ART regimen (n=12)

Randomization will be stratified by HIV-1 RNA level ($\leq 100,000$ copies/mL and $> 100,000$ copies/mL) at screening.

Subjects enrolled in Part 1 who do not successfully complete the study drug doses in Part 1 will not continue onto Part 2 of the study.

Subjects enrolled in Part 1 who do not show a reduction in HIV RNA $> 0.5 \log_{10}$ from baseline to Part 2 Day 1 will have an Early Study Drug Discontinuation (ESDD) visit within 72 hours of laboratory results being available. They will have study medications discontinued and will not continue to Part 2.

Part 2 (Sentinel Cohort 1): GS-9131 + BIC + DRV+ RTV Regimen

In Part 2, subjects in Sentinel Cohort 1 will start a regimen consisting of GS-9131 (60 mg) + BIC (30 mg) + DRV+RTV (800 mg/100 mg) for 24 weeks. CCI

Part 2: GS-9131 + BIC + TAF Regimen (Subjects in Sentinel Cohort 2 and Randomized Cohorts)

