All subjects who successfully complete all study drug doses in Sentinel Cohort 2 and the Randomized Cohorts will discontinue study drug from Part 1 on Day 15. To continue to Part 2, subjects must have a $> 0.5 \log_{10}$ decline in plasma HIV-1 RNA from their pre-GS-9131 baseline in the 14 days of functional monotherapy. Since this result will not be immediately available at the completion of Part 1, all subjects completing Part 1 will continue on their failing regimen until results are available. Results will be available no later than 9 days after completion of Part 1. Subjects who meet criteria will proceed to Day 1 of Part 2. Any subjects in the Sentinel Cohort, and Treatment Arms A, B and C who do not meet the criterion for $> 0.5 \log_{10}$ decline in plasma HIV-1 RNA from their pre-GS-9131 baseline will not continue to Part 2. All subjects in Treatment Arm D will be eligible to continue to Part 2. In Part 2, subjects from the Sentinel Cohort 2 and the Randomized Cohort will start a regimen consisting of GS-9131 (up to 180 mg) + BIC (75 mg) + TAF (25 mg) as described below.

- Treatment Arms A-C: GS-9131 (up to 180 mg)+ BIC + TAF
- Sentinel Cohort 2 and Treatment Arm D: GS-9131 180 mg + BIC + TAF

At Week 8, subjects who have plasma HIV-1 RNA < 200 copies/mL or who have an HIV-1 RNA ≥ 200 copies/mL and a reduction in HIV-1 RNA $> 1 \log_{10}$ from baseline at any study visit will continue study medications.

Subjects who have a confirmed sub-optimal virologic response at Week 8 defined as plasma HIV-1 RNA ≥ 200 copies/mL and reduction in HIV-1 RNA $\leq 1 \log_{10}$ from baseline at all study visits up to Week 12 may be discontinued from the study and further optimization of their ARV regimen if feasible will be done by the Investigator. Subjects meeting criteria for sub-optimal virologic response as further defined in Section 6.10.1 will be contacted for an ESDD visit and discontinued from the study within 72 hours of results being available.

Subjects with protocol-defined virologic failure and evidence of treatment emergent resistance to any component of their regimen at any time will be discontinued from the study drug and treated with an ARV regimen chosen by the Investigator. For additional information, please reference ESDD (Section 6.4.1).

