5.3. Dosage and Administration of GS-9131, BIC, DRV, RTV, TAF and PTM GS-9131

Study drug GS-9131, BIC, DRV, RTV, TAF, and PTM GS-9131 tablets will be provided by Gilead.

In Sentinel Cohort 1, subjects will begin assigned GS-9131 60 mg once daily. All other ARVs in the current regimen will be continued. All ARVs, including GS-9131, will be administered by directly observed therapy (DOT) on Days 1-10. If the current regimen includes ARVs taken more than once daily, taken at night, or with certain meals, additional doses will be documented

by the subject in a dosing diary provided for the study. GS-9131 must be administered by DOT on Days 1-10. Subjects who successfully complete all study drug doses through Day 10 and show a reduction in plasma HIV RNA $> 0.5 \log_{10}$ from their pre-GS-9131 baseline during functional monotherapy will discontinue their current failing regimen, and start an optimized regimen consisting of GS-9131 (60 mg) + BIC (30 mg) + DRV (800 mg) + RTV (100 mg) for 24 Weeks.

In Sentinel Cohort 2 and the Randomized Cohort, Part 1, subjects will begin assigned GS-9131 doses up to 180 mg, or PTM once daily. All other ARVs in the current regimen will be continued. All ARVs, including GS-9131, will be administered by directly observed therapy (DOT) on Days 1-14. If the current regimen includes ARVs taken more than once daily, taken at night, or with certain meals, additional doses will be documented by the subject in a dosing diary provided for the study. GS-9131 must be administered by DOT on Days 1-14.

Subjects in Sentinel Cohort 2 and Randomized Cohort Treatment Arms A-C who successfully complete all study drug doses in Part 1 and show a reduction in plasma HIV RNA $> 0.5 \log_{10}$ from their pre-GS-9131 baseline during functional monotherapy will enroll in Part 2, discontinue their current failing regimen, and start an optimized regimen consisting of GS-9131 (up to 180 mg) + BIC (75 mg) + TAF (25 mg). The GS-9131 dose in the combination regimen will be defined by the open-label or randomization dose given in Part 1. Reduction of plasma HIV RNA $> 0.5 \log_{10}$ from baseline must be demonstrated at Day 15. Dose of GS-9131 for the Randomized Cohort will be determined following review of Sentinel Cohort 2. The dose of GS-9131 for the OLE will be determined following review of the safety, efficacy and available PK data of the Randomized Cohort in Part 1 from Part 2.

CCI

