All subjects who successfully complete all study drug doses in Part 1 and meet criteria to proceed to Part 2 will transition to Part 2 and discontinue their current failing regimen.

The following evaluations are to be completed on Day 1 of Part 2. The Investigator must have confirmed eligibility before proceeding with the Part 2 Day 1 visit. The subject must complete all study procedures before being administered the study drug. Initiation of treatment with the study drug must take place within 24 hours after the Day 1 visit.

- Review concomitant medications
- Record any SAEs and all AEs related to protocol mandated procedures occurring after signing of the consent form
- Complete physical examination (urogenital/anorectal exams will be performed at the discretion of the Investigator)
- Vital signs measurement (blood pressure, pulse, respiration rate, and temperature), including weight
- Obtain blood and urine samples as described in Sections [6.8.1](#), [6.8.2](#), [Appendix 2](#), and [Appendix 3](#)
- Document study drug dispensation and accountability for all study drugs dispensed
 - Subjects must be reminded to take study drug at the same time each day with food

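### The IDMC safety trigger for the Randomized Cohort counts only subjects later assigned to Part 2, so events that stop drug during Part 1 dosing are almost always left out

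*Protocol*

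**What the plan says.** **The trigger.** Section 6.5.1 opens the Randomized Cohort and Part 2 rule with "If 2 or more subjects in Part 1 of the Randomized Cohort who are subsequently assigned to treatment cohorts in Part 2 experience". The synopsis (Protocol-Specific Stopping Rules) reads "If 2 or more subjects in the Randomized Cohort who are subsequently assigned to treatment cohorts in Part 2 experience". In both, two kinds of event qualify: a Grade 3 or 4 treatment-emergent AE that ends study drug, and an SAE the investigator considers possibly related. The consequence is an IDMC review of the accumulated safety data.

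**What stops drug.** The by-subject rule in Section 6.5.1 ends dosing for a possibly related Grade 3 or 4 AE or confirmed laboratory abnormality, "or any serious adverse event (SAE) considered to be possibly related to study drug".

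**Who enters Part 2.**
- Section 3.3: "Subjects enrolled in Part 1 who do not successfully complete the study drug doses in Part 1 will not continue onto Part 2".
- Section 5.3 admits those in "Randomized Cohort Treatment Arms A-C who successfully complete all study drug doses in Part 1" who also show the required viral decline.
- Section 6.3.2 (Part 2 Day 1): "All subjects who successfully complete all study drug doses in Part 1 and meet criteria to proceed to Part 2 will transition".
- For placebo, Section 3.3 says "All subjects in Treatment Arm D will be eligible to continue to Part 2", but the synopsis has Arm D start the Part 2 regimen "once daily for 24 weeks after successful completion of Part 1".

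**The concern.** A safety trigger should respond to the events that worry the investigators most, which here are those serious enough to end dosing. This one makes a subject's event count only if she later goes on to Part 2, and ending dosing in Part 1 is what keeps her out of Part 2. Part 2 assignment is also unknown during Part 1 dosing, because Section 3.3 allows up to 9 days after Part 1 for the HIV-1 RNA result. The count therefore cannot be kept in real time.

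The setting gives this some weight. Section 1.8.1 states that there are no clinical safety data at 180 mg and relies on animal margins; Table 1 puts the margins for GS-9131 itself at 0.5 to 0.8 in monkey, rabbit and dog. Sentinel Cohort 2 adds at most 10 subjects at that dose before randomization. Section 1.9 cites by-cohort stopping rules among the protections, and this trigger is the only event-driven group rule for the Randomized Cohort. The Sentinel rule carries no Part 2 condition.

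**Working it through.** The plan gives no operating characteristic for the trigger, so there is no stated figure to reproduce. The check is one of rule logic, followed by an illustration of size.

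**Logic, for a qualifying event during Part 1 dosing**
1. AE limb: the event counts only if it ends study drug. If it does so in Part 1, the doses are not completed.
2. SAE limb: a possibly related SAE ends dosing under the by-subject rule, so again the doses are not completed.
3. Incomplete Part 1 dosing bars entry to Part 2 (Sections 3.3, 5.3 and 6.3.2; the synopsis for Arm D).
4. A subject not assigned to Part 2 is not counted.

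**Possible ways round**
- *Withhold and resume after a related Grade 3 event (Section 7.6.2).* This does not help: Section 7.6 gives the Section 6.5 criteria precedence and, where rules differ, applies the more conservative one.
- *SAE judged related only after the last Part 1 dose.* A genuine exception: the doses are complete and the subject may go on.
- *Unrelated Grade 3 AE continued on drug (allowed by Section 7.6.2) that leads to discontinuation in Part 2.* Also a genuine exception, since the AE limb can be read as carrying no relatedness condition.

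The result is *almost always* left out, not *always*.

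**Illustration**

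Inputs: three GS-9131 arms of 12, n = 36 (synopsis, Section 3.3); threshold 2 (Section 6.5.1). The per-subject rate p of a qualifying on-dosing event is an assumption, because the documents give none at 180 mg. Let q be the share of subjects with such an event who still enter Part 2. Subjects are taken as independent with a common rate.

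Without the filter, P(X ≥ 2) = 1 − (1−p)^36 − 36p(1−p)^35:
- p = 0.02: 1 − 0.4832 − 0.72 × 0.4931 = 0.16
- p = 0.05: 1 − 0.1578 − 1.80 × 0.1661 = 0.54

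As written, replace p by pq:

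| p | no filter | q = 0 | q = 5% | q = 10% |
|---|---|---|---|---|
| 2% | 0.16 | 0 | 0.0006 | 0.002 |
| 5% | 0.54 | 0 | 0.004 | 0.014 |

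The logic above puts q at about 0; the last two columns allow for leakage through the exceptions. If the 12 placebo subjects had the same event rates, n = 48 and the no-filter values would be 0.25 and 0.70.

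**The case against.** The best answer is that little depends on this sentence. It prompts a review and halts nothing. Each affected subject is still stopped individually. SAEs reach the sponsor within 24 hours (Section 7.3.2). The synopsis has the IDMC meet once the Randomized Cohort has completed Part 1, and Section 8.10 lets the IDMC convene earlier if it chooses. The section heading names both the Randomized Cohort and Part 2, which suggests a drafting slip, and the SAP reports no randomized-cohort efficacy data.

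Most of this stands and limits the consequence, but none of it repairs the trigger. By-subject stopping and SAE reporting work case by case. The post-Part 1 meeting comes after Part 1 dosing has ended and is missing from Section 8.10. Earlier meetings are discretionary.

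Three stronger readings are tempting and not supported:
- *The count is skewed toward placebo.* A reader might infer this because GS-9131 subjects without the viral decline are excluded while Arm D faces no virologic test. But a subject whose event stops Part 1 dosing is already out, whatever her viral load, so those exclusions do not measure this defect.
- *Sentinel subjects in Part 2 have no group rule.* Section 6.5.1 limits the Sentinel rule to Part 1, but the synopsis version has no such limit. This is a conflict between two texts, not an established gap.
- *Nothing from the Randomized Cohort can ever count.* The two exceptions, and events in Part 2 among those who go on, may count.

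**Conclusion.** The concern holds on the wording. For events that stop study drug during Part 1 dosing, the trigger is close to inoperative: about 0 as written, against 0.16 and 0.54 at assumed event rates of 2% and 5% in 36 GS-9131 subjects. Those probabilities are illustrative; the conclusion rests on the by-subject rule and the dose-completion condition, not on them.

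The likely effect is a later IDMC review. A reader might infer that toxicity would go unreviewed, or that participants in this study were affected; the documents support neither. SAP Section 2.4 says the study stopped on the Sentinel Cohort 2 criterion, and SAP Section 6 reports no efficacy data from the Randomized Cohort. The defect is in the plan as written, and it should be fixed because the correction is cheap.

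**What to change.** In Section 6.5.1 and the synopsis, replace the description of who is counted with *subjects dosed in the Randomized Cohort (Part 1) or in Part 2*. Leave the threshold, qualifying events and consequence unchanged.

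Separately, reconcile the Sentinel rule, limited to Part 1 in Section 6.5.1 but not in the synopsis, so that it is clear which group rule covers Sentinel rollovers in Part 2. SAP Section 2.4 counts 4 subjects in Part 2, and SAP Table 8-1 lists only Sentinel rollovers there, so the question is a practical one.

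The cost is one phrase changed in two places and one clarification, with no extra subjects or data. The downside is possibly more IDMC reviews. The probabilities above indicate the scale for Part 1 only; they do not include Part 2 exposure of at least 24 weeks.
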